Clinical status assessment per WHO 9-point scale ⁶		X	X	X	X	X	X	X	X	X	X	X	X	X	X	
Viral presence and viral load by central testing ⁷		X	X (sentinel only) ⁷	X (sentinel only) ⁷	X (sentinel only) ⁷			X							X	
Confirmation of COVID-19 diagnosis by PCR	X ²	X (PR) ²														

Assessment ¹	Time point	SCR	Treatment Period											FU ¹⁴		ET
			-3d to -1d	D1 (base-line)	D2	D3	D4	D5	D6	D7	D8	D10	D12	D14	D21 (± 3d)	D28 (± 3d)
Oxygenation and FiO ₂ ⁸		X	X	X	X	X	X	X	X	X	X	X	X	X	X	X
Safety assessments:																
Physical examination		X														X
Weight/height ⁹		X													X	X
Hematology, chemistry safety labs ⁶		X	X	X			X			X	X			X	X	X
CRP ⁶		X														
Urinalysis ¹⁰		X								X						
Urine or serum β-hCG (female subjects only)		X ¹¹												X		X
ECG ¹²		X								X						
HR, BP, RR, temperature ⁸		X	X	X	X	X	X	X	X	X	X	X	X			X
(S)AEs ¹³								X								X
Concomitant medications (including SOC)										X						X

AE = adverse event; BP = blood pressure; COVID-19 = novel coronavirus; HR = heart rate; P = pre dose; PAO₂ = partial pressure of oxygen; PR – pre-randomization; RR = respiratory rate; sent = sentinel; SOC = standard of care; SCR = screening.

Note: All screening assessments are to be performed before dosing. If procedures required at any time point have already been performed as part of routine clinical care, these assessments do not need to be repeated, and information will be collected and entered on the eCRF from the subject's medical records. Unscheduled visits can take place at any time at the discretion of the site to check for new AEs/SAEs or to repeat key missed assessments or for other reasons.

¹ The order of assessments can be performed at the discretion of the investigator once informed consent is obtained.

² COVID-19 diagnosis to be confirmed by local testing (PCR) before randomization and first dosing. Saliva, swab, or sputum testing may be used based on local standard of care.

³ To be performed while hospitalized based on standard-of-care local assessment. Evidence of pulmonary involvement consistent with COVID-19 may also be obtained from clinical examination, per the judgment of the investigator. Evidence of pulmonary involvement obtained by clinical examination should be documented in the eCRF.

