⁴ PK assessments will be performed as a substudy in all sentinel subjects. For those subjects requiring dialysis, a single pre- and post-dialysis PK should be obtained for review by the DMC to decide if dose adjustment is needed. PK should be measured weekly for 2 weeks at C_{max} (4-5 hours post dose) for subjects with renal insufficiency when possible.

⁶ Assessments for clinical/respiratory status, progression, and safety serum chemistry and hematology tests to be performed and samples to be collected while hospitalized based on standard-of-care local laboratory assessments and after discharge from the hospital by home visit or outpatient clinic visit or telemedicine call. For subjects who are discharged to home or other outpatient setting after initial hospitalization, the assessments and laboratory samples can be obtained less often but not less than at least once weekly. CRP result required to determine eligibility are based on local laboratory results at screening.

⁷ Viral load testing will be collected daily for the first 4 days using central testing in the first 10 enrolled subjects as part of the sentinel safety assessment at select sites. For all subjects, including the sentinel subjects, swabs, saliva, or other sample collection (as specified in the Study Manual) for central viral load testing will be collected on D1 pretreatment and on D7 or earlier if being discharged from the hospital prior to D7.

Fulcrum Therapeutics
Protocol FIS-001-2020

Losmapimod

⁸ Vital signs will be performed after subjects have been supine for at least 5 minutes when possible. Vital signs to include oxygen saturation; PaO₂ should be recorded if available from blood gases obtained as part of SOC; oxygen administration should also be recorded (eg, room air or oxygen flow by nasal canula or facial mask or endotracheal tube). For subjects who are discharged to home or other outpatient setting after initial hospitalization, assessments may be obtained less often but at least once per week in the outpatient clinic or at home.

⁹ Height assessed at screening only; can be by self-report or from medical records. Weight is an actual recording.

¹⁰ Urinalysis will be performed during the study period only on Day 7 and on any other day only if clinically indicated.

¹¹ Pregnancy testing to be conducted within 72 hours of the first dose of study treatment.

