All study visits during the first week of treatment are anticipated to be conducted in the inpatient setting. If the clinical status of the subject improves such that the clinician discharges the subject from the hospital before the end of the study, the follow-up assessments will be conducted on an outpatient basis by alternative methods, including the use of local laboratories/facilities or home visits for blood draws, telemedicine, and/or outpatient follow-up clinic visits as deemed clinically appropriate per COVID-19 follow-up standard of care (SOC) at each site (refer to [Section 6.7](#)).

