8.11 Type I error for testing key study endpoints

The overall Type I error of the study will be controlled at 0.025 for 1-sided tests of hypotheses for the following key study endpoints, using an appropriate alpha control method:

1. Proportion of progressors to death or respiratory failure by Day 28
2. Change in clinical status using the 9-point WHO scale at Day 14
3. Change in clinical status using the 9-point WHO scale at Day 7
4. Oxygen-free days by Day 28

Further details on the methodology will be provided in the SAP.

Fulcrum Therapeutics
Protocol FIS-001-2020

Losmapimod

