3.1.8 Handling of Dropouts and Missing Data

All missing or incomplete safety and PD data, including dates and times, will be treated as such. Missing test results or assessments will not be imputed, and as such, are assumed missing completely-at-random (MCAR).

For laboratory data, values below the limit of quantitation (recorded as “< LLQ”) will be set to half that limit.

For the analysis of hospital-free and ICU-free days, subjects who die prior to the analysis time point will have post-death days considered to be not hospital-free and not ICU-free.

Adverse events with missing start dates will be considered as treatment-emergent unless the partial date excludes that possibility, e.g., the adverse event month is prior to the first dose of study drug. Otherwise, the first day of the month will be used to impute missing start days and January will be used to impute missing start months. For example, if the first dose of study drug was on January 8, 2021 and an adverse event started in January 2021 with missing day, the start date will be imputed as the first dose date (January 8, 2021) and this adverse event will be considered as treatment-emergent. In the same example, if another adverse event has start month of December 2020 with missing day (before the first dose date of January 8, 2021), its start date will be imputed as December 1, 2020 and will not be considered as treatment-emergent.

Subjects who terminate the study prior to the analysis time point, not due to death, will be considered as missing for the analysis of key efficacy endpoints. Missing data in each treatment arm will be imputed using the observed data in their respective arm under the missing at random (MAR) assumption. Multiple imputation (MI) will be performed using the fully conditional specification (FCS) model. The imputation model will include the stratification factors, sex, and baseline CRP.

The handling of missing data for the key efficacy endpoints are outlined as the following:

1. Primary endpoint: patients whose status could not be ascertained (lost-to-follow up, etc.) will be imputed using multiple imputation approach.
2. Change in Clinical Status at Days 7 and 14: missing clinical status at the post-baseline timepoint will be imputed using multiple imputation approach.

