3.4 Efficacy Assessment

3.4.1 Primary Efficacy Endpoint

3.4.1.1 Primary Analysis

The primary efficacy endpoint is the proportion of subjects who progress to death or respiratory failure by Day 28.

Respiratory failure is defined as either need for mechanical ventilation (invasive or non-invasive) or high flow oxygen (defined by greater than 15 LPM flow of oxygen to maintain oxygen saturation between 90% and 95%), sustained for at least 48 hours, at any time during the study.

The fitted logistic regression model is used to predict the response rate for every subject in the study as if they had received the treatment or the control intervention.

Assuming p_t is probability of outcome in the losmapimod arm; p_c is the probability of outcome in the control arm

Study hypothesis: $H_0: p_t - p_c = 0$

$H_1: p_t - p_c < 0$

Assuming $p_t=0.18$, $p_c=0.30$, we can restate the hypothesis as

$H_0: \theta = \theta_0 = 0$

$H_1: \theta = \theta_1 = -0.12$

where θ is calculated as $p_t - p_c$. For the final analysis, the proportion of subjects achieving the primary endpoint in the treatment arms will be compared using an adjusted risk difference obtained from the logistic regression model, adjusted for stratification factors, sex, and baseline CRP. Sample SAS codes are provided in Appendix A. More details can be found in Guo et al. (2012) and Ge et al. (2011).

An interim analysis to assess futility analysis—and potential sample size re-estimation—will be conducted, as discussed in Section 5.1.

All results will be summarized descriptively by treatment arm and expressed as proportions, along with corresponding unadjusted/adjusted 95% CI of the difference between response rates, and p-values.

In the first step of multiple imputation, data will be multiple imputed using the FCS discriminant function separately by treatment arm to 20 imputed datasets. This analysis assumes data are missing at random. The imputation model will include the stratification factors, sex, baseline CRP, and a two-level binary factor (discharge from the hospital prior to discontinuing the study; Yes, No). [REDACTED]

For each imputed dataset, the proportion of subjects achieving the primary endpoint in the treatment arms will be compared using an adjusted risk difference obtained from the logistic regression model, adjusted for stratification factors, sex, and baseline CRP for each imputed dataset.

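### Discharged subjects need a WHO score only once a week on no named day, so Day 14 (and less so Day 7) scores may be missing selectively in recovered subjects, and the SAP's imputation does not clearly use hospital status on that day

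*Protocol*

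**What the plan says.** Table 1 of protocol Version 3.0 schedules the WHO score on both Day 7 and Day 14, but the row carries footnote 6: "Clinical status assessment per WHO 9-point scale ⁶". That footnote has assessments continue "after discharge from the hospital by home visit or outpatient clinic visit or telemedicine call" and then relaxes their frequency for discharged subjects: "the assessments and laboratory samples can be obtained less often but not less than at least once weekly". It does not say which days the weekly contacts fall on. Table 1 prints ±3 days for Day 21 and Day 28 and nothing for Day 7 or Day 14. The SAP text supplied has no rule for assigning an off-day score to either day.

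Protocol 8.11 lists "Change in clinical status using the 9-point WHO scale at Day 14" second among the key endpoints and the Day 7 version third. SAP 3.1.5 tests them in that fixed order.

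On missing scores, SAP 3.1.8 says "missing clinical status at the post-baseline timepoint will be imputed using multiple imputation approach", within arm and under missing at random, and "The imputation model will include the stratification factors, sex, and baseline CRP". SAP 3.4.1.1, for the primary endpoint, adds "a two-level binary factor (discharge from the hospital prior to discontinuing the study; Yes, No". SAP 3.4.2 then says that missing data for the endpoints listed before that sentence, WHO status among them, are handled in a similar way to the primary endpoint. It sets a missing score after death to 8. There is no matching rule for a subject known to be at home, although Protocol 6.3.1 records the date of discharge and condition at discharge.

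**The concern.** The relaxation applies only to people who have left hospital, that is, to those with true scores of 0 to 2. Any score lost through it is lost because the subject recovered. An imputation model built on stratification factors, sex and baseline CRP cannot see that. It would fill the gap from observed subjects in the same arm, among whom inpatients are over-represented.

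The percentages in each WHO category, and the risk differences built on them, would then be shifted towards worse status. Information would also be lost on two endpoints in the confirmatory sequence, although a telephone call on the right day would supply it.

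**Working it through.** **Inputs.** From the documents: 205 subjects per arm (Protocol 8.1.1) and the provisions above. The plan gives no discharge rate, missingness rate or power figure for the WHO endpoints, so it has no figure of its own to reproduce on this point. Its one sample-size figure, 410 subjects for about 80% power on the primary endpoint, does reproduce. With 30% against 18%, looks at 103 and 205 per arm and boundaries z = −0.67873 and −1.91358, power is 0.802 and one-sided type I error 0.0250. That figure is not affected here.

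Everything below rests on stated assumptions.

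**1. Can footnote 6 be met with no Day 14 score?** Yes, taking the footnote alone. A subject discharged on Day 9 and called every seven days is assessed on Days 9, 16 and 23.

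**2. How often would a strict weekly pattern hit the day?** Simulation, assuming discharge on a day uniform from Day 2 to the day before the target, a last inpatient score on that day, and then one score every 7 days at random phase. Share of discharged subjects with a score in the window:

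| Window | Day 7 | Day 14 |
|---|---|---|
| exact day | 14% | 15% |
| ±1 day | 55% | 47% |
| ±2 days | 83% | 76% |
| ±3 days | 100% | 100% |

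**3. What would imputation without hospital status do?** Let d be the true share discharged and m the share of discharged subjects whose score is missing. If the covariates say nothing about discharge, the share discharged after imputation is d(1 − m)/(1 − dm).

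Take d = 0.60 on placebo and a common odds ratio of 1.6. The losmapimod odds are (0.60/0.40) × 1.6 = 2.4, so d = 2.4/3.4 = 0.706. With m = 0.20:

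- Placebo: 0.48/0.88 = 54.5%
- Losmapimod: 0.5647/0.8588 = 65.8%

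The common odds ratio below comes from a large-sample proportional-odds fit without covariates, on status collapsed to six levels (0–2, 3, 4, 5, 6–7, 8). Subjects not discharged are split 25/30/20/12/13% over the last five.

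| m placebo / losmapimod | Scores missing overall | Discharged after imputation, placebo / losmapimod | Common odds ratio |
|---|---|---|---|
| 0 / 0 | 0% | 60.0% / 70.6% | 1.60 |
| 20% / 20% | 13% | 54.5% / 65.8% | 1.59 |
| 40% / 40% | 26% | 47.4% / 59.0% | 1.58 |
| 86% / 86% | 56% | 17.6% / 25.5% | 1.41 |
| 20% / 30% | 17% | 54.5% / 62.7% | 1.41 |
| 30% / 20% | 16% | 51.2% / 65.8% | 1.80 |

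With 40% to 80% of placebo subjects discharged, the odds ratio ranges over 1.59–1.60 (20% in both arms), 1.41–1.50 (86% in both), 1.40–1.43 (20%/30%) and 1.75–1.82 (30%/20%).

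The pattern has a simple cause. For discharged against not discharged, the odds ratio after imputation is 1.6 × (1 − m on losmapimod)/(1 − m on placebo). It is unchanged when m is equal, and becomes 1.40 or 1.83 for the two unequal cases. At very high equal m, thinning only the discharged category breaks proportional odds and pulls the common estimate down.

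**4. Worst case.** If every site calls weekly from discharge, one discharged subject in seven has a score on Day 14, so the observed share is (1 − d) + d/7.

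- d = 0.70: 0.300 + 0.100 = 0.400, so 60% missing. Imputed share still in hospital 0.300/0.400 = 75%, against a true 30%.
- d = 0.78: 0.220 + 0.111 = 0.331, so 67% missing. Imputed share still in hospital 0.220/0.331 = 66%, against a true 22%.

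The variance of the discharged/in-hospital log odds ratio is proportional to 1/d + 1/(1 − d) summed over arms (10.59) with full data, and to 7/d + 1/(1 − d) (26.85) with observed data. The standard error ratio is √(26.85/10.59) = 1.59.

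**The case against.** Several provisions point the other way:

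- Table 1 still schedules the score on Days 7 and 14. The footnote relaxes how often, and the obvious weekly subset of the printed days is 7, 14, 21 and 28.
- Protocol 5.4.3 and SAP 2.2.2 foresee a Day 14 visit for bottle collection, in or out of hospital.
- Table 1 footnote 12 sets a Day 7 ECG for all subjects, and Protocol 3.1 states: "All study visits during the first week of treatment are anticipated to be conducted in the inpatient setting".
- Telemedicine is allowed, and unscheduled contacts may be used to repeat missed key assessments.
- Scores missing after death are set to 8, so the worst outcomes are kept.
- The ranked tests use the ordinal model. The category risk differences are not in the sequence.
- Text after the discharge factor is redacted, the sample code is not in the supplied text, and the Study Manual and programming specifications are separate documents.

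Much of this stands. A reader might infer that these scores will be missing in most recovered subjects, that missing at random fails by design, and that the ranked comparisons are therefore biased. The documents do not support that. Off-schedule calling is possible under the text, not prescribed by it. Day 7 is clearly less exposed than Day 14. At moderate missingness that is equal between arms, the odds ratio hardly moves.

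The permission itself remains. Footnote 6 is the express exception to the schedule for this row. Neither bottle collection nor an ECG calls for a WHO score. Inpatient care in week 1 is an expectation, and footnote 7 provides for discharge before Day 7. The discharge factor in 3.4.1.1 is worded around discontinuing the study. Its value for a discharged subject who is still on study but lacks a score is undefined, and 3.1.8 omits it.

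**Conclusion.** The concern holds as a gap in wording that may cost data selectively. A compliant site can have no Day 14 score for discharged subjects. The SAP gives two differing accounts of the imputation model, and neither clearly carries hospital status on the analysis day.

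The size depends on rates the documents do not give. With 20% of discharged subjects missing in both arms and no discharge status in the model, the discharged shares are understated by about 5 points (60.0% to 54.5%, 70.6% to 65.8%) and the odds ratio is essentially intact. Material distortion of the odds ratio needs very high missingness or a difference between arms, and nothing in a blinded trial's documents points to the latter. The 60% and 67% missing in step 4 are a worst case that requires sites generally to pass over the scheduled Day 14 assessment; they are not a forecast. The primary endpoint's sample size is not affected by this point.

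The change is still worth making, because it only fixes the days of contacts already required and uses data already recorded.

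**What to change.** **Protocol, Table 1 footnote 6.** State that for discharged subjects the minimum weekly contacts fall on Days 7, 14, 21 and 28, by telephone or telemedicine if needed, with a WHO score at each. Print a narrow window for Days 7 and 14, for example ±1 day. A narrow window without fixing the contact days is not enough: under strict weekly contact, ±1 day captures only 47% at Day 14. A ±3-day window would capture all, but some of the scores it accepts would be the last inpatient one.

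**SAP 3.1.8.** Reconcile it with 3.4.1.1 and 3.4.2 so that there is one imputation model for WHO status. Either include hospital status on the analysis day in that model, or restrict imputed scores to 0–2 for subjects known to be out of hospital that day. With status on the day in the model, the discharged share is not shifted.

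**Cost.** Footnote and SAP wording, and slightly less scheduling freedom for sites. No additional contacts are required beyond the weekly minimum.

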2 STUDY OBJECTIVES AND ENDPOINTS

All study objectives will be evaluated in subjects diagnosed with COVID-19.

Objectives	Endpoints
Primary	
To assess the efficacy of losmapimod compared with placebo for treatment of COVID-19 when administered concurrently with standard of care	Proportion of progressors to death or respiratory failure by Day 28
Secondary	
To evaluate the effect of losmapimod compared with placebo on clinical outcomes	
Clinical status by Days 7 and 14 as measured on the 9-point WHO ordinal scale (WHO 2020):
 
• (8) death• (7) ventilation plus additional organ support (vasopressors, renal replacement therapy, ECMO)• (6) Intubation and mechanical ventilation• (5) noninvasive ventilation or high-flow oxygen therapy• (4) oxygen therapy but not requiring high-flow or non-invasive ventilation• (3) hospitalized but not requiring oxygen therapy• (2) Discharged from the hospital but with limitation of activities• (1) Discharged from the hospital and without any limitation• (0) No clinical evidence of the disease
To assess the effect on clinical status of treatment with losmapimod compared with placebo	
Total number of study days free of oxygen supplementation by Day 28
 
Total number of study days in ICU by Day 28
 
Total number of study days hospitalized by Day 28
 
Total number of respiratory failure-free study days by Day 28

Fulcrum Therapeutics
Protocol FIS-001-2020

Losmapimod

Objectives	Endpoints
	Percentage of subjects discharged from the hospital by Day 28
To assess the effect on survival following treatment with losmapimod compared with placebo	All-cause mortality at Day 28 Number of study days alive by Day 28
To assess the safety and tolerability of losmapimod compared with placebo	Incidence of AEs and SAEs Incidence of clinically significant changes in laboratory parameters and vital sign measurements
To characterize changes in SARS-CoV-2 infection following treatment with losmapimod compared with placebo	Quantifiable viral RNA on Day 7

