Percentages of subjects will be tabulated by treatment arm, along with differences between treatment arms, at each time point. The proportion of subjects will be compared using an adjusted risk difference obtained from a logistic regression model, adjusting for stratification factors, sex, and baseline CRP.

Standard survival analysis methods will be used as sensitivity analyses to compare the time to each of these clinical events of interest (death and respiratory failure) as well as the composite thereof. Specifically, the cumulative incidence rates between two groups at Day 28 will be compared, accounting for potential differential follow-up.

Incidence of AEs/SAEs by Day 28: will be summarized by system organ class and preferred term and by treatment arm using percentages.

Incidence of AEs/SAEs is calculated by the number of subjects who developed AEs/SAEs during the study divided by the sum of the number of subjects who completed the study and the number of subjects who died during the study period. (see above edit)

Incidence of clinically significant changes by Day 28: Percentage of subjects with clinically significant changes in laboratory parameters, ECG, and vital sign measurements will be computed for each treatment arm along with associated 2-sided 95% Clopper-Pearson CI.

Changes in the assessments will be considered as clinically significant if the Baseline assessment is not clinically significantly abnormal and there has been at least one occurrence of post-Baseline assessments with a clinically significant abnormal result by Day 28.

[figure not shown]
Death is not considered a form of missing data or censoring. The incidence of clinically significant changes is calculated by the number of subjects with clinically significant changes during the study divided by the sum of the number of subjects who completed the study and the number of subjects who died during the study period.

Clearance of quantifiable viral RNA by Day 7: percentages of subjects with clearance of quantifiable viral RNA will be tabulated by treatment arm, along with differences between treatment arms, at each time point. The proportion of subjects will be compared using an adjusted risk difference obtained from a logistic regression model, adjusting for stratification factors, sex, and baseline CRP.

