Change from baseline in viral RNA will be summarized by treatment arm and also analyzed using an analysis of covariance (ANCOVA) model with fixed effects of treatment, and stratification factors, sex and baseline CRP as covariates.

Death is not considered a form of missing data or censoring. The proportion of subjects with clearance of quantifiable viral RNA by Day 7 is calculated by the number of subjects with clearance of quantifiable viral RNA by Day 7 divided by the sum of the number of subjects who is in study by Day 7 and the number of subjects died by Day 7.

The endpoint of comparing percentage of subjects discharged from the hospital, all-cause mortality by Day 28, incidence of AEs/SAEs, incidence of clinically significant changes, and percentage of subjects with clearance of quantifiable viral RNA by Day 7 between treatment groups will be analyzed similarly as the primary endpoint.

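### The Day 7 viral sample moves forward for subjects discharged before Day 7, and the SAP does not account for it, so clearance is understated and the arm comparison can be distorted.

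*Protocol*

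**What the plan says.** The objective is stated for a fixed day: "Quantifiable viral RNA on Day 7" (Protocol Section 2). Collection is not fixed. Under Table 1 footnote 7 of Version 3.0, samples for "central viral load testing will be collected on D1 pretreatment and on D7 or earlier if being discharged from the hospital prior to D7". Table 1 schedules no later viral sample except at early termination. The first 10 (sentinel) subjects are also sampled daily over the first four days, so for nearly all subjects this is the only post-baseline result.

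SAP 3.4.2 analyses a slightly different quantity: "Clearance of quantifiable viral RNA by Day 7: percentages of subjects with clearance of quantifiable viral RNA will be tabulated by treatment arm". The arms are compared with an "adjusted risk difference obtained from a logistic regression model, adjusting for stratification factors, sex, and baseline CRP". The denominator is "the sum of the number of subjects who is in study by Day 7 and the number of subjects died by Day 7". Change from baseline in viral RNA is also "analyzed using an analysis of covariance (ANCOVA) model with fixed effects of treatment, and stratification factors, sex and baseline CRP as covariates". Neither model refers to when the sample was taken. SAP 3.3.4 labels the viral time points Day 1 and Day 7, with exceptions only for the sentinel group and early termination.

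Protocol 3.1 anticipates first-week visits in hospital. For subjects who leave, it plans follow-up "including the use of local laboratories/facilities or home visits for blood draws, telemedicine, and/or outpatient follow-up clinic visits".

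**The concern.** Discharge happens after randomisation, and the trial itself treats it as an outcome: days hospitalised and percentage discharged are secondary endpoints. A subject discharged and sampled on Day 3 has 2 days after baseline in which to clear virus, where an inpatient sampled on Day 7 has 6. The early-discharged subject is still in the study at Day 7. On the natural reading of the SAP denominator, a positive early sample is therefore counted as not cleared by Day 7, although nobody looked on Day 7.

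Two things follow. Clearance is understated in each arm that has early discharges. If the arms differ in how many leave early, or how early, they are observed for different lengths of time, and the comparison mixes viral kinetics with discharge timing. The ANCOVA is more exposed: an early negative still counts correctly as cleared by Day 7, but an early viral-load value simply misses any later decline. Reduced viral load in coronavirus models is part of the stated rationale (Protocol 1.1, item 2), so readers will look at this result.

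**Working it through.** **No plan figure to reproduce.** The documents give no expected clearance rate, no share discharged before Day 7 and no power for this endpoint. All discharge and clearance rates below are assumptions. The 205 per arm is from Protocol 8.1.1.

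**General formula.** Let e be the share of an arm sampled early, and q the share of those sampled early who are still positive but would clear by Day 7. Observed clearance falls short of true Day 7 clearance by e × q. With P for placebo and T for losmapimod, the bias in the difference (losmapimod minus placebo) is eP·qP − eT·qT.

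**Clearance model.** Constant hazard from Day 1: F(t) = 1 − exp(−h(t − 1)), with h set so that F(7) equals the assumed Day 7 clearance c. Arm rate = (1 − e)·c + e·F(early day). The drug has no effect on clearance unless stated.

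**Worked case.** c = 50%, so F(5) = 37.0% and F(4) = 29.3%.
- Placebo, 40% sampled on Day 5: 0.6 × 0.50 + 0.4 × 0.370 = 44.8%.
- Losmapimod, 50% sampled on Day 4: 0.5 × 0.50 + 0.5 × 0.293 = 39.6%.
- Spurious difference: −5.2 points. The standard error with 205 per arm is √(0.448 × 0.552/205 + 0.396 × 0.604/205) = 4.9 points.

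**Range around it.** With c = 30%, 50% and 70%, and three discharge patterns (30% on Day 5 vs 40% on Day 5; 40% on Day 5 vs 50% on Day 4; 40% vs 60%, both on Day 4), the difference runs from −0.9 to −6.5 points. The arms fall 3 to 15 points below the true rate.

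**Smaller discharge shares, same early day in both arms** (c = 30% or 50%, Day 4 to 6):

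| Early share, placebo vs losmapimod | Spurious difference (points) |
|---|---|
| 20% vs 20% | 0 |
| 20% vs 30% | −0.4 to −2.1 |
| 20% vs 40%, or 30% vs 50% | −0.9 to −4.1 |

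Across these cases a two-sided 5% test with 205 per arm rejects in 5.0% (equal shares) to 13.6% of trials.

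**Faster recoverers also clear faster.** If 40% of subjects are fast recoverers whose clearance hazard is 1.5 to 4 times that of the others (c = 40% for the others), and the drug only brings discharge forward (20% vs 40% early, Day 4 or 5), the difference is −2.5 to −5.0 points.

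**Drug truly speeds clearance.** With hazard ratio 1.5, 20% vs 40% early on Day 4 or 5, and c = 30% or 50% on placebo, a true benefit of 11.4 to 14.6 points is observed as 7.0 to 11.4 points. It is attenuated, not reversed.

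**Limit on the sign.** Take eP = 20%, eT = 30% and qP = 30%.

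| qT | Bias (points) |
|---|---|
| 30% | 0.06 − 0.09 = −3.0 |
| 20% | 0.06 − 0.06 = 0 |
| 10% | 0.06 − 0.03 = +3.0 |
| 0% | 0.06 − 0 = +6.0 |

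**With a Day 7 sample in everyone,** e = 0 in both arms and the bias is 0.

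**The case against.** The strongest reply is that the direction is not established. A reader might infer that the comparison must be biased against whichever arm is discharged sooner. The documents do not support that. It requires early discharge to differ between arms and early-discharged positives to convert at similar rates in both; the last table shows zero or reversed bias when they do not. Equal discharge timing gives no differential bias. This stands.

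A reader might also infer that a clinically effective drug would appear to impair viral clearance. That is too strong: where the drug also speeds clearance, the cases computed show attenuation, and even the −5.2 point case is about one standard error.

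The SAP reading is partly inference. No sentence says that a discharge sample is the Day 7 result, and the Study Manual, to which collection details are deferred, is not available. SAP 3.4.2 also says that viral clearance is analysed similarly to the primary endpoint, which brings in multiple imputation. But imputation helps only if an early positive is declared missing, and nothing declares it so. The discharge factor in the imputation model of SAP 3.4.1.1 concerns subjects who discontinue the study.

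Finally, sampling before discharge is a pragmatic way to secure a specimen, and Protocol 3.1 expects week 1 to be inpatient. Both are fair. Yet footnote 7 itself provides for earlier discharge, and subjects on room air are eligible, so some early discharge is to be expected.

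**Conclusion.** The point holds in this form: sampling time depends on a post-randomisation outcome, and the SAP neither recognises nor handles that. Clearance by Day 7 is understated wherever some early-discharged positives would have cleared by Day 7. If one arm is discharged sooner, its clearance and its fall in viral RNA will probably be understated more. Over the assumed ranges the spurious difference is about 0 to 6 points. The size rests wholly on assumed discharge and clearance rates, and the sign on similar conversion rates in the two arms. With only a pre-discharge sample, the trial's own data could not show which case applied.

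The consequence is limited. Viral clearance is a secondary endpoint outside the four alpha-controlled endpoints of SAP 3.1.5. The primary endpoint, interim analysis and sample size are untouched. This is an inexpensive improvement, not a threat to the trial's main conclusion.

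**What to change.** **Protocol, Table 1 footnote 7.** Collect a Day 7 sample, with a stated window, in every subject, by saliva or swab. For discharged subjects, take it at a Day 7 home or outpatient contact. Keep the discharge sample as an extra. Saliva is already permitted, home and outpatient sampling is already planned, and footnotes 10 and 12 already place a urinalysis and an ECG on Day 7. The contact must be written in as in-person, because footnote 6 requires only weekly contact after discharge and allows a telemedicine call.

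**SAP 3.4.2, clearance.** Count an early negative as cleared by Day 7. Treat a positive taken before the window, with no later sample, as unknown at Day 7 and not as not cleared. Handle it by multiple imputation that includes Day 1 viral load, the early result and its day, and discharge status, or use an interval-censored time-to-clearance analysis.

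**SAP 3.4.2, change in RNA.** Restrict the ANCOVA to samples in the Day 7 window, with the others imputed in the same way. Do not add sampling day as a covariate: treatment may affect it. Do not discard every early sample either, since early negatives are informative.

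**Wording.** Reconcile on Day 7 (objectives) with by Day 7 (analysis).

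**Cost.** Saliva kits for subjects discharged in week 1, footnote and SAP text, and some missing Day 7 values. If few discharged subjects supply a Day 7 sample, the imputation will lean on those still in hospital, and that assumption should be stated.
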